2.1.6 Efficacy Studies

2.1.6.1 Efficacy As a Single Agent

Different doses of pretomanid, given as a single agent, were evaluated in 2 studies [23, 29]. In the first study, doses of 200, 600, 1000, and 1200 mg/day were used [23]. In the second study, lower doses including 50, 100, 150, and 200 mg/day were used [29]. Both studies produced a measurable decrease in sputum CFU counts over the 14-day treatment period. The results, summarized in [Table 2](#), indicate that there were no meaningful differences among the pretomanid dose groups of 200 to 1200 mg/day also supported by formal dose trend analyses. There was a dose-related trend with respect to changes in mean logCFU values over time in the second study, with a smaller reduction seen in the 50 mg/day dose group compared with the 100, 150, or 200 mg/day dose groups. This latter study, however, was not powered to detect significant differences between the dose groups.

2.1.6.2 Efficacy When Administered in a Multidrug Regimen

Three Phase 2 studies evaluated pretomanid efficacy in a multidrug regimen [18, 30-32]. The treatment regimens studied, and results are summarized in [Table 2](#). The first multidrug regimen [30] compared 6 regimens:

- BDQ (alone).
- BDQ + pyrazinamide.
- pretomanid + BDQ.
- pretomanid + pyrazinamide.
- pretomanid + moxifloxacin + pyrazinamide.
- standard treatment regimen (INH, rifampin, pyrazinamide, and ethambutol).

In this trial, the mean daily rate of decline in logCFU in the first 14 days of treatment was highest for pretomanid + moxifloxacin + pyrazinamide combination. The second multidrug regimen [32] was a 7-arm study of the following treatments:

- pretomanid + BDQ + pyrazinamide + clofazimine.
- pretomanid + BDQ + pyrazinamide.
- pretomanid + BDQ + clofazimine.
- BDQ + pyrazinamide + clofazimine.
- pyrazinamide alone.
- clofazimine alone.
- standard treatment with INH, rifampin, and pyrazinamide.

The study showed that a regimen containing pretomanid + BDQ + pyrazinamide resulted in a marked daily rate of decline in logCFU (mean 0.167) comparable to standard treatment (mean 0.151), indicating that the pretomanid-containing regimen is a potential new TB treatment regimen. In the third trial, 3 regimens were compared, and the mean daily rate of decline of logCFU with a regimen containing pretomanid 200 mg + moxifloxacin + pyrazinamide was significantly greater than standard treatment (0.155 vs 0.112, respectively) [31].

2.1.6.3 Efficacy on Drug-Resistant TB

In a Phase 2 trial by Dawson et al [31], 26 patients with MDR-TB were treated with pretomanid + moxifloxacin + pyrazinamide. The mean daily rate of decline in logCFU over 56 days in MDR-TB patients was comparable to treatment-naïve patients treated with standard treatment (0.117 vs 0.112, respectively). These results indicate that pretomanid is useful for treatment of MDR-TB.

A Phase 3, pivotal, open-label trial Nix-TB assessed the safety, tolerability, efficacy, and PK of BPaL regimen in the treatment of patients with either pulmonary XDR-TB or TI/NR MDR-TB. A total of 109 patients aged 17 to 60 years old with pulmonary XDR-TB or TI/NR MDR-TB were enrolled at 3 centers in South Africa. Patients received study treatment for a minimum of 6 months (i.e., until Week 26). If patients were culture positive or reverted to being culture positive between Month 4 and Month 6 and their clinical condition suggested they may have ongoing TB infection, the study treatment may have been extended to 9 months (i.e., Week 39) or the patient may have been withdrawn from the trial. The primary endpoint was the incidence of an unfavorable outcome, defined as treatment failure (bacteriologic or clinical) or disease relapse. Clinical treatment failure was defined as a change from the protocol-specified TB treatment as a result of a lack of clinical efficacy, retreatment for TB, or TB-related death through follow-up until 6 months after the end of treatment. The success rate was 89% at 6-month post end of treatment. FDA and EMA approval of pretomanid, in the context of the BPaL regimen, was based on the Nix-TB data [33].

Table 2: Summary of Phase 2 studies using Pretomanid

| Outcome measure | N* | Regimens | Results | Conclusions | Ref. |
|--|----|------------------------------|-------------------|--|------|
| Single Agent | | | | | |
| Daily rate of decline in logCFU over 14 days (Mean \pm SD) | 69 | Pretomanid 200 mg | 0.098 \pm 0.07 | Outcome measure the same for all 4 pretomanid dosages. | [23] |
| | | Pretomanid 600 mg | | | |
| | | Pretomanid 1000 mg | | | |
| | | Pretomanid 1200 mg | | | |
| | | Standard (HRZE) [‡] | 0.148 \pm 0.055 | | |
| Daily rate of decline in logCFU over 14 days (Mean \pm SD) | 69 | Pretomanid 50 mg | 0.063 \pm 0.058 | -Dose-related trend with a smaller reduction seen in the 50 mg/day group. -Study not powered to detect significant differences between the dose groups. | [29] |
| | | Pretomanid 100 mg | 0.09 \pm 0.073 | | |
| | | Pretomanid 150 mg | 0.078 \pm 0.074 | | |
| | | Pretomanid 200 mg | 0.112 \pm 0.070 | | |
| | | Standard (HRZE) [‡] | 0.177 \pm 0.042 | | |
| Multidrug Regimen | | | | | |
| Daily rate of decline in logCFU over 14 | 85 | Bedaquiline | 0.061 \pm 0.068 | -The mean decline in CFU in pretomanid + moxifloxacin + pyrazinamide group was significantly higher than the decline in all other groups | [30] |
| | | Bedaquiline + pyrazinamide | 0.131 \pm 0.102 | | |
| | | Pretomanid + Bedaquiline | 0.114 \pm 0.050 | | |

| Outcome measure | N* | Regimens | Results | Conclusions | Ref. |
|--|-----|---|--------------------------|--|------|
| days (Mean \pm SD) | | Pretomanid + Pyrazinamide | 0.154 ± 0.040 | except pretomanid + pyrazinamide and standard treatment groups. | |
| | | Pretomanid + Moxifloxacin + Pyrazinamide | 0.233 ± 0.128 | | |
| | | Standard (HRZE) [‡] | 0.14 ± 0.094 | | |
| Daily rate of decline in logCFU over 14 days, Mean (95% CI) | 105 | Pretomanid + Bedaquiline + Pyrazinamide + Clofazimine | 0.115 (0.039-0.189) | This regimen is a potential new TB treatment. | [32] |
| | | Pretomanid + Bedaquiline + Pyrazinamide | 0.167 (0.075-0.257) | | |
| | | Pretomanid + Bedaquiline + Clofazimine | 0.076 (0.005-0.145) | | |
| | | Bedaquiline + Pyrazinamide + Clofazimine | 0.124 (0.035-0.214) | | |
| | | Pyrazinamide | 0.036 (-0.026-0.099) | | |
| | | Clofazimine | -0.017 (-0.085-0.053) | Clofazimine has no activity alone. | |
| | | Standard (HRZE) [‡] | 0.151 (0.071-0.232) | | |
| Daily rate of decline in logCFU over 56 days, Mean (95% Bayesian credibility interval) | 207 | Pretomanid (100 mg) + Moxifloxacin + Pyrazinamide | 0.133 (0.109-0.155) | -Daily CFU decline significantly greater than that for standard treatment. -Only MDR-TB patients included. -Daily reduction in CFU was comparable to that of standard treatment for patients with drug-susceptible TB. | [31] |
| | | Pretomanid (200 mg) + Moxifloxacin + Pyrazinamide | 0.155 (0.133-0.178) | | |
| | | Standard (HRZE) [‡] | 0.112 (0.093-0.131) | | |
| | | Pretomanid (200 mg) + Moxifloxacin + Pyrazinamide | 0.117 (0.070-0.174) | | |

CI=confidence interval; CFU=colony forming unit; HRZE=standard treatment with isoniazid, rifampin, pyrazinamide, and ethambutol; MDR-TB=multidrug-resistant tuberculosis; TB=tuberculosis.

*N includes all volunteers randomized to the different study groups. [‡], Standard (HRZE) indicates standard treatment with isoniazid, rifampin, pyrazinamide, and ethambutol.

[§]All pretomanid doses were once daily and all-pretomanid doses were 200 mg unless specified. Unless specified, all studies were on treatment-naïve patients with pulmonary TB.

2.2 Scientific Rationale

2.2.1 Purpose of Study

TB is a major public health problem worldwide. Treatment of drug-susceptible TB requires the use of 4 first-line anti-TB drugs for at least 6 months [4]. New drug treatments may help shorten the duration of treatment and potentially increase patient compliance, and therefore, have a direct impact on the control of TB. Furthermore, MDR and XDR-TB have made the prevalence of TB more challenging. Up to 50% of MDR-TB cases fail treatment and treatment outcome of XDR-TB is unpredictable [1], indicating that development of new anti-TB drugs is an essential component of TB control.

Pretomanid is one of a few anti-TB drugs with the following unique and attractive characteristics:

1. It has early bactericidal and sterilizing activity, with a potential to shorten the duration of treatment for drug-susceptible TB [23, 24]. It shortens the duration of treatment for MDR-TB in the context of the BPaL regimen [33],
2. It has excellent activities against both drug-sensitive and MDR-isolates of Mtb [26],
3. It has been shown to have a low incidence of AEs in multiple clinical trials [18],
4. It has narrow spectrum of activity limited primarily to Mtb with no significant activity against a broad range of Gram-positive and Gram-negative bacteria [34],
5. It has no demonstrable cross resistance to a variety of anti-TB drugs [25],
6. It is administered orally [18, 19], and
7. It neither inhibits nor is metabolized by major CYP450 enzyme isoforms except for CYP3A4 in vitro, importantly indicating a low potential for drug-drug interactions, including with presently used antiretrovirals for treatment of HIV [35, 36].

Patients with renal impairment, particularly severe renal impairment or end stage renal disease (ESRD), may have an increased risk of drug exposure and may require lower doses of certain drugs compared to patients with normal renal function [37]. According to FDA and Europe, the Middle East, and Africa (EMEA) guidelines, a PK study should be carried out during the development phase of a new drug that is likely to be used in patients with renal dysfunction and whose pharmacokinetics are likely to be significantly altered in renally impaired patients [38, 39]. Less than 1% of

unmetabolized pretomanid is excreted in the urine. [18]. Therefore, like other commonly used anti-TB drugs such as ethambutol and pyrazinamide, which are at least partly eliminated through kidneys, the PK of pretomanid must be studied in patients with CKD. CKD is a very common clinical disease with estimated prevalence of 8 to 16%, and CKD patients globally, particularly those in advanced stages, have significantly increased risk of developing TB [11-13].

Regarding pretomanid metabolites, no single metabolic pathway can be considered major. Two metabolites have been selected for quantification: M19 (4-Trifluoromethoxybenzoic acid) and M50 (hydroxy imidazole). In one mass-balance study, M19 was the largest drug-derived metabolite, representing up to 35% of the sample radioactivity at 24 hours post-dose. However, it has no activity or toxicity. In another mass-balance study, M50 was found to account for 6.3% of the parent area under the AUC and it has been identified as potentially genotoxic based on an in vitro Ames test. In 2 mouse genotoxicity studies, no genotoxicity was observed up to a 2000 mg/kg dose. In a recently completed carcinogenicity study in transgenic mice with M50 exposure 2-3 times the expected human exposure, no pretomanid-related deaths, tumors, or gross necropsy findings were seen. There is no evidence suggestive of any potential carcinogenic hazard in rat toxicity studies up to 6 months and in monkey toxicity studies up to 9 months. No metabolites have been found to represent more than 13% of the total dose in urine and feces. Therefore, based on results from previous studies and expected excretion in urine, measuring the plasma exposures of pretomanid metabolites (M50 and M19) in this patient population will be valuable.

The results from this study will help determine future dosing and frequency of administration of pretomanid that can be safely used in patients with different stages of renal impairment.

2.2.2 Study Population

The study population will be representative of participants with varying degrees of renal disease as defined by eGFR as well as participants who are healthy matched controls. Children will not be included as this study is designed for adult participants between the ages of 18-85 years (for detailed information see [Section 5.1 Eligibility Criteria](#)).

2.3 Potential Risks and Benefits

2.3.1 Potential Risks

The potential risks of this trial are those associated with having blood drawn, adverse reactions to pretomanid, and breach of confidentiality.

Potential adverse drug reactions include mild to moderate nausea and vomiting, mild to moderate rash, and increased transaminases. These are listed as adverse drug reactions in the pretomanid IB [18].

In pooled Phase 1 trials (i.e., pooled data from all Phase 1 studies in healthy volunteers) where pretomanid was dosed as single or multiple doses, the most frequently observed AEs were headache and nausea.

A study on the effects of pretomanid in healthy volunteers determined that increases in creatinine were noted at high repeat doses in healthy volunteers. A follow-up intensive renal function study revealed that the drug does not adversely affect GFR, renal plasma flow, or filtration fraction but appeared to decrease tubular renal secretion of creatinine. A single dose of pretomanid did not affect kidney function in healthy participants and it is not anticipated that kidney function will change from a single dose.

Testicular toxicity is considered as a potential risk based on pre-clinical studies. TB Alliance is currently conducting a study to further investigate pretomanid and testicular toxicity. A single dose of pretomanid is however, not anticipated to have an impact on testicular function in general.

After administering the pretomanid, patients will be closely observed and asked about any new symptoms before each blood draw. Clinical evaluation will be done when necessary, during the first 24 hours of hospital admission, and during follow-up visits. Life-threatening side effects, although not anticipated, will be reported immediately to the hospital emergency medical team and standard procedures will be followed. Volunteers with serious side effects identified during the follow-up visits will be transported to the Emergency Department (ED) of the local hospital where they will be examined by an ED physician and admitted to the hospital for further management if required.

To limit possible adverse reactions to study participants, volunteers who donated blood or blood products >500 mL within 30 days from screening or who plans to donate during the study or up to 14 days after dosing will be excluded from the study.

Blood Draw

Drawing blood may cause transient discomfort and fainting. Fainting is usually transient and managed by having the participant lie down and elevate his/her legs. Bruising at the blood draw site may occur but can be prevented or lessened by applying pressure to the blood draw site for a few minutes after the blood is taken. Rarely, drawing blood may cause infection (thrombophlebitis). The use of aseptic (sterile) technique will make infection at the site where blood will be drawn extremely unlikely.

Peripheral Catheter (if needed)

Inserting a peripheral catheter may cause pain, bleeding, hematoma, vein irritation, infiltration, extravasation, phlebitis, air embolism, and/or infection. Use of proper aseptic technique during the insertion provides protection against infection.

Pregnancy

It is unknown if the study drug poses any risks to an unborn child. As such, females of childbearing potential, i.e., women who have started menses, must agree to use an effective method of birth control for the duration of the study ([Section 5.1.1](#)). Males who are sexually active with a female of childbearing potential must agree not to father a child or donate sperm for the duration of the study.

Other Risks

Personal Health Information (PHI)

Participants will be asked to provide PHI. All attempts will be made to keep this PHI confidential within the limits of the law. However, there is a chance that unauthorized persons will see the participants' PHI. All study records will be kept in a locked file cabinet or maintained in a locked room at the participating sites. Electronic files will be password-protected. Only people who are involved in the conduct, oversight, monitoring, or auditing of this trial will be allowed access to the PHI that is collected. Any publications from this trial will use de-identified information. Organizations that may inspect and/or copy research records maintained at the participating site for quality assurance and data analysis include groups such as the local Institutional Review Boards (IRBs), National Institute of Allergy and Infectious Diseases (NIAID), and FDA.

As required by US law, a description of this clinical trial will be available on <https://clinicaltrials.gov/ct2/show/NCT03896750>. This website will not include information that can be used to identify participants. At most, this website will include a summary of the results.

There may be other risks, discomforts, or side effects that are unknown at this time.

2.3.2 Potential Benefits

There is no direct benefit to participants who will receive the study product. This study is a PK study in patients with renal impairment. Patients with renal impairment have a higher risk of developing TB and participation will not prevent or reduce the risk of contracting TB. The results from this study will help determine the safe and effective dose of pretomanid for treatment of TB in patients with renal impairment. Pretomanid, in the context of the BPaL regimen, shortens the treatment of TI or NR MDR and XDR-TB to 6 months.

3 STUDY DESIGN, OBJECTIVES, AND ENDPOINTS OR OUTCOME MEASURES

3.1 Study Design Description

This is a Phase 1, open-label, single-dose, sequential group study to evaluate the PK and safety profile of pretomanid in participants with renal impairment (excluding those with ESRD needing dialysis) compared to matched participants with normal renal function.

The study will be conducted following a reduced PK study design in Part A, see [Table 1](#) and [Figure 1](#). Part A will enroll participants from Group 1A (i.e., 6 healthy matched controls) and Group 2 (i.e., 6 participants with severe renal impairment and ESRD, not on dialysis).

A decision to proceed to Part B will be made after the PK of pretomanid and safety of participants enrolled in Part A have been reviewed. If Part A demonstrates at least a 50% increase in pretomanid AUC in Group 2 (severe renal impairment and ESRD, not on dialysis) relative to the exposures in Group 1A (matched participants with normal renal function), then the reduced PK study will extend to the full PK study to enroll participants into Part B (i.e., to investigate mild and moderate renal impairment) and all enrollment will be initiated concurrently in Part B groups (1B, 1C, 3, and 4). Otherwise, no further study is recommended.

Study Population

Part A

Group 1A: 6 healthy participants (matched controls) with normal renal function: MDRD (eGFR ≥ 90 mL/min). Participants will be matched by race, gender, age (± 10 years, but between 18 to 85 years of age) and body mass index (BMI) (18 to 40 kg/m²).

Group 2: 6 severe renal impairment participants: Stage 4, MDRD (eGFR 15-29 mL/min), and ESRD not on dialysis, Stage 5, MDRD (eGFR < 15 mL/min).

Part B

Groups 1B and 1C: 6 healthy participants (matched controls) each, for Groups 3 and 4, respectively: MDRD (eGFR ≥ 90 mL/min). Participants will be matched by race, gender, age (± 10 years, but between 18 to 85 years of age) and BMI (18 to 40 kg/m²).

Group 3: 6 mild renal impairment participants: Stage 2, MDRD (eGFR 60-89 mL/min).

Group 4: 6 moderate renal impairment participants: Stage 3, MDRD (eGFR 30-59 mL/min).

3.2 Study Objectives

3.2.1 Primary

- To evaluate the PK profiles of pretomanid in plasma and urine after a single oral dose of 200 mg in participants with renal impairment compared to matched healthy controls.

3.2.2 Secondary

- To assess the safety profile of a single oral dose of 200 mg pretomanid in renally impaired participants to matched healthy controls.
- To evaluate the PK profiles of representative pretomanid metabolites (M19 and M50) in plasma and urine.

3.3 Study Endpoints or Outcome Measures

3.3.1 Primary

3.3.1.1 Plasma PK of Pretomanid (see [Section 10.5](#) for specific PK parameters)

The plasma PK of a single dose of pretomanid will be assessed from serial blood samples collected up to 1 hour pre-dose (Day 1) and at multiple time points post dosing: 1, 2, 4, 5, 6, 8, 12, 16, 24, 36, 48, 72, and 96 hours. The primary outcome measure will be total plasma concentration of pretomanid.

3.3.1.2 Urine PK of Pretomanid (see [Section 10.5](#) for specific PK parameters)

The urine PK of a single dose of pretomanid will be assessed from urine collected up to 1 hour pre-dose, 0-4, 4-8, 8-12, 12-24, 24-48, 48-72, and 72-96 hours post-dose. Volume of urine will be measured and recorded at each of these time intervals. Urine samples will be stored at room temperature and then frozen at -20°C within 24 hours. Urine samples will be stored in ≤ 100 mL aliquots at -20°C until shipped to Fisher Bioservices for storage.

The concentrations of pretomanid in plasma and urine will be measured by the validated bioanalytical methods. The pretomanid PK profiles in plasma and urine estimated through a non-compartmental analysis.

3.3.2 Secondary

- Safety – Number of participants reporting AEs. (Time Frame: Time of dosing [Day 1] to Day 12).
- Safety – Mean change from baseline in hemoglobin (Hgb), alanine aminotransferase (ALT), aspartate aminotransferase (AST), total bilirubin, blood urea nitrogen (BUN), creatinine (includes eGFR), serum potassium and magnesium (Time Frame: Screening [Days -28 to -7], Day 5 and Day 12).
- Safety – Mean change from baseline in oral temperature, pulse, and sitting blood pressure (Time Frame: Day 1 [pre-dose], 12 hours, 24 hours, 48 hours, 72 hours, 96 hours, and Day 12).
- Safety – Mean change from baseline in ECG corrected QT interval by Fridericia (QTcF) (Time Frame: Screening [Days -28 to -7] and Day 5).
- The concentrations of pretomanid metabolites (M19 and M50) in plasma will be measured by validated bioanalytical methods. PK – area under the plasma concentration-time curve from time 0 to the last measurement (AUC_{last}), and any other parameters considered to be of interest, of representative metabolites M19 and M50 in plasma (Time Frame: Up to 96 hours post-dose).
- Excretion of representative metabolites M19 and M50 in urine. The amounts of M19 and M50 will be calculated in urine (i.e., M19 and M50 concentrations measured using validated bioanalytical methods multiplied by collected urine volume).

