2.1.5.2 Pharmacokinetics

The Investigator Brochure (IB) [18] includes data from the Phase 1 studies in healthy volunteers and Phase 2 studies in participants with pulmonary TB. These data indicate that the PK profile for pretomanid following oral dosing was consistent for healthy participants and participants with pulmonary TB. In both populations, pretomanid was readily absorbed after oral administration and slowly eliminated from plasma. Pretomanid plasma concentrations increased in a dose-dependent manner after single-dose administration of up to 1000 mg in healthy participants and participants with TB, but the increase was less than dose proportional, particularly at doses above 200 mg/day. The hypothesis that absorption decreases (i.e., is saturated) at high doses of pretomanid was further supported by the observations that mean apparent clearance (CL/F) and volume of distribution (V_d/F) at steady-state (Day 7) values increased with dose, while the mean elimination half-life (t_{1/2}) values remained similar across dose levels. This suggests that the apparent lack of dose proportionality in exposure is most likely related to the decreased bioavailability with increasing dose.

In both healthy participants and participants with pulmonary TB, steady-state concentrations of pretomanid in plasma were achieved within approximately 5 days of once-daily dosing, and the accumulation factor was approximately 2. Both findings support the observed elimination t_{1/2} of approximately 18 hours in healthy participants and participants with pulmonary TB. The mean peak concentration (C_{max}) and AUC from time 0 to 24 hours (AUC_{0-24hr}) values following a 200 mg dose of pretomanid in participants with pulmonary TB ranged from 1.1 to 1.2 µg/mL and 17 to 19 µg·hr/mL, respectively, after single-dose administration and from 2.2 to 2.4 µg/mL and 38 to 40 µg·hr/mL, respectively, after 14 days of dosing.

Based on the IB [18], pretomanid is moderately absorbed following oral administration, with a T_{max} of 4 to 5 hours after single- or multiple-dose administration under fasted conditions. Dosing with a high-calorie, high-fat meal increased the T_{max} by approximately 1 hour, and the drug exposure was about half in the fasted state comparing with that in the fed state. It is recommended that the clinical dose of 200 mg be administered in the fed state.

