6.3 Follow-Up

6.3.1 Visit 01M, Day 4, Time 72 Hours ± 4 Hours Post-dose, Clinic Visit or Continued Hospital Stay, per Site Decision

- Interim medical history, including an assessment for new medical conditions and stability of chronic diseases, will be obtained by interview of participants and any changes since the previous visit will be noted.
- A targeted physical examination may be performed if indicated based on review of interim medical history, by a study clinician licensed to make medical diagnoses and listed on the Form FDA 1572 as the site PI or sub-investigator.
- All concomitant medications will be recorded on the appropriate DCF.
- Vital signs, including oral temperature, sitting blood pressure, and sitting pulse will be obtained. Participants must not eat or drink anything hot or cold within 10 minutes prior to taking oral temperature.
- Receive home urine collected jug from subject. Measure and record urine PK volume, aliquot, label and freeze per [Section 7.2.2.1](#).
- Provide urine PK collection container and remind the participant to collect urine at home and keep urine container at room temperature with cap on for PK.
- Approximately 4 mL of venous blood will be collected for PK.
- All AE/SAEs will be recorded on the appropriate DCF/DMID SAE Report Form.

6.3.2 Visit 01N, Day 5, Time 96 Hours ± 4 Hours Post-dose, Clinic Visit or Continued Hospital Stay, per Site Decision

- Interim medical history, including an assessment for new medical conditions and stability of chronic diseases, will be obtained by interview of participants and any changes since the previous visit will be noted.
- A targeted physical examination may be performed if indicated based on review of interim medical history, by a study clinician licensed to make medical diagnoses and listed on the Form FDA 1572 as the site PI or sub-investigator.
- All concomitant medications will be recorded on the appropriate DCF.
- Vital signs, including oral temperature, sitting blood pressure, and sitting pulse will be obtained. Participants must not eat or drink anything hot or cold within 10 minutes prior to taking oral temperature.
- A 12-Lead ECG will be performed.
- Receive home urine collected jug from subject. Measure and record urine PK volume, aliquot, label and freeze per [Section 7.2.2.1](#).
- Approximately 4 mL of venous blood will be collected for PK.
- All AE/SAEs will be recorded on the appropriate DCF/DMID SAE Report Form.

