Vital sign measurements must include the participant's sitting pulse, sitting blood pressure (mm Hg), and oral body temperature (°F) at the screening Visit 00A, 01A, 12, 24, 48, 72, and 96 hours and Day 12 or at ET after study product administration. Height and weight will be obtained at screening Visit 00A only. If a physiologic parameter, e.g., vital signs, is outside of the protocol-specified range (for control participants) or outside the patient's baseline (for renally impaired participants), then the measurement may be repeated once if, in the judgment of the investigator, the abnormality is the

result of an acute, short-term, rapidly reversible condition (e.g., stress, anxiety, or “white coat syndrome”). The participant’s baseline is the latest vital sign recorded in their electronic health record (EHR) in the last 3 months before screening. For participants with CKD but no vital signs recorded in their EHR, the protocol-specified range used for control participants will be used. Once participants are dosed, the vital signs measured at Visit 01A will be considered their baseline. A physiologic parameter may also be repeated if there is a technical problem with the measurement caused by a malfunction, or an inappropriate measuring device (i.e., inappropriate-sized blood pressure cuff). If there is an abnormal blood pressure measurement, the participant should lay down for 10 minutes and then the measurement should be repeated while the participant is awake and resting supine. For analyzing secondary safety endpoints in rescreened participants (if any) and that include a comparison to screening baseline values should have the rescreening values as baseline.

In addition, a 12-lead ECG will be performed at Screening Visit 00A and Visit 01N. If at Visit 01N the ECG is abnormal, it can be repeated.

At subsequent visits, assessment for AEs and SAEs will occur and the participant will be interviewed about interim AEs/SAEs and medical history.

Participants will be admitted for multiple blood draws following oral administration of study product. Any AEs/SAEs will be recorded on the appropriate DCF/DMID SAE Report Form prior to discharge from the hospital.

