9.9 Other Safety Measures

An ECG will be performed at the Screening Visit 00A and Visit 01N. If the result is abnormal, it may be repeated per the investigators discretion. The ECG intervals (QTcF), including change from baseline, will be summarized at the Screening Visit 00A and Visit 01N (96 hours \pm 4 hours post-dose), including any repeated ECG measurements, using descriptive statistics ([Table 79](#)).

Individual ECG interval measurements will be provided in [Listing 15](#).

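### The only scheduled post-dose ECG is at 96 h, when about 3% of peak pretomanid remains at normal elimination, so the QTcF endpoint carries little information about QT near peak exposure

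*Protocol*

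**What the plan says.** The endpoint in Protocol Section 3.3.2, "Mean change from baseline in ECG corrected QT interval by Fridericia (QTcF"), has a two-point time frame: "QTcF) (Time Frame: Screening [Days -28 to -7] and Day 5". Protocol Section 7.1 gives the matching schedule: "In addition, a 12-lead ECG will be performed at Screening Visit 00A and Visit 01N". Section 6.3.2 places the second of these at "Visit 01N, Day 5, Time 96 Hours ± 4 Hours Post-dose". Protocol Section 10.5.3.4 summarizes QTcF at the same two visits, and SAP Section 9.9 agrees: "An ECG will be performed at the Screening Visit 00A and Visit 01N".

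The written procedures for the dosing day, the rest of the hospital stay, Visit 02 and early termination list no ECG. The one addition is a repeat of the same tracing: "If at Visit 01N the ECG is abnormal, it can be repeated". Unscheduled visits (Protocol Section 6.6) are for clinical reasons and are not part of the endpoint.

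The SAP shell for this endpoint is numbered Table 80 in Appendix 1 (Section 9.9 cites it as Table 79). It gives the change from baseline with a 90% CI. ECG data also go into the interim safety and PK review that informs whether Part B proceeds (Protocol Section 10.4.1, SAP Section 6.6).

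Protocol Section 2.1.5.2 reports a Tmax "of 4 to 5 hours after single- or multiple-dose administration under fasted conditions", about 1 h later after a high-fat meal, and a half-life "of approximately 18 hours in healthy participants and participants with pulmonary TB". Section 4.3 has every participant dosed fed.

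**The concern.** The trial is run because exposure may be raised in renal impairment, and the plan treats QT as relevant: a QTc of 460 msec or more and a family history of long-QT syndrome are exclusions in both populations. Yet QTcF is measured about 90 h after the expected peak. Participants are in-house with a PK sample due at 5 h and 6 h (Protocol Sections 6.2.5 and 6.2.6), close to the expected peak, and no ECG is taken then.

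The risk is one of interpretation. A 90% CI lying close to zero at 96 h could be taken as evidence about QT at high exposure in renal impairment, although the measurement was made after most of the drug had gone. Neither document states this limit.

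**Working it through.** **Inputs.** From Protocol Section 2.1.5.2: half-life about 18 h; fasted Tmax 4-5 h, plus about 1 h with food, so about 5-6 h; CL/F about 8 L/h; Vd/F about 175 L; accumulation factor about 2. From Section 6.3.2: ECG at 96 ± 4 h. The documents give no predicted 96 h concentration and no precision figure for QTcF, so there is no stated figure to reproduce.

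**Step 1, simple decay from peak.** Fraction of peak = 2^(-(96 - Tmax)/t½).
- Tmax 5 h: 2^(-91/18) = 3.0%.
- Tmax 6 h: 2^(-90/18) = 2^(-5) = 3.1%.
- Over the 92-100 h window: 2.6-3.7%.

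**Step 2, one-compartment oral model.** C(t) is proportional to [ka/(ka - k)] × (e^(-kt) - e^(-ka·t)), with k = ln2/t½ and ka solved from Tmax = ln(ka/k)/(ka - k). At 18 h, ka is 0.581 per h (Tmax 5 h) or 0.447 per h (Tmax 6 h). The model gives 3.2-3.4% of peak at 96 h, and 2.8-4.0% over the window.

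**Step 3, other half-lives.**
- From clearance and volume: ln2 × 175/8 = 15.2 h.
- From the accumulation factor with 24 h dosing: 1/(1 - 2^(-24/t½)) = 2 gives t½ = 24 h.
- Renal scenarios (assumption: AUC rises through lower clearance alone, volume unchanged): AUC up 50% gives 18 × 1.5 = 27 h; up 100% gives 18 × 2 = 36 h. The first is the Part B threshold and the second is the sample-size scenario in Protocol Section 10.2.

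| Half-life | Simple decay at 96 h, Tmax 5-6 h | One-compartment model at 96 h |
|---|---|---|
| 15.2 h | 1.6% | 1.7-1.8% |
| 18 h | 3.0-3.1% | 3.2-3.4% |
| 24 h | 7.2-7.4% | 7.6-7.9% |
| 27 h | 9.7-9.9% | 10.3-10.7% |
| 36 h | 17.3-17.7% | 18.3-19.0% |

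In the last two rows the model holds ka at its 18 h value, so the peak moves to between 5.6 and 7.4 h.

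**Step 4, what this does to an effect.** Suppose, for illustration only, an effect of 10 ms at peak, proportional to concurrent parent concentration. At 96 h it would be 10 × 0.03 = 0.3 ms at the 18 h half-life, and 10 × 0.19 = 1.9 ms at most in the doubled-AUC scenario.

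**Step 5, is the in-house time near peak?** At t½ 18 h:
- Tmax 5 h: C(6)/C(5) = (0.7937 - 0.0306)/(0.8249 - 0.0547) = 99%.
- Tmax 6 h: C(5)/C(6) = (0.8249 - 0.1070)/(0.7937 - 0.0684) = 99%.

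With clearance halved and the peak as late as 7.35 h, C(6)/Cmax = 0.8225/0.8306 = 99% and C(5)/Cmax = 0.8012/0.8306 = 96%. Either visit serves.

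**The case against.** **This is not the drug's QT study.** Protocol Section 2.1.5.1 refers to a thorough QT study in the Phase 1 program. Here QTcF is one of several safety endpoints, summarized descriptively with no formal test, and no section says it is meant to detect an effect at peak. This stands, and it sets the scope. A reader might infer that QT with pretomanid has gone unexamined; the documents do not support that. They do not report that study's QT results either, so it does not make this endpoint informative in renal impairment.

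**A late effect is not excluded.** A reader might infer that the endpoint must show no change whatever the drug does. That holds only if QT follows concurrent parent concentration. Protocol Section 2.1.5.2 says most of the dose becomes metabolites and that total radioactivity leaves the blood slowly. No passage links a metabolite to QT, and Section 2.2.1 describes M19 as inactive, but there are no data on a delayed or metabolite-driven effect. The condition therefore has to be stated. Equally, the documents offer no such reason for choosing 96 h.

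**About 3% is the normal-elimination case.** This is correct. The participants of most interest may retain 10-19%. That is still far below peak.

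**Moving the ECG does not make the endpoint strong.** The baseline remains a screening ECG 7-28 days before dosing, and a 5-6 h tracing follows a high-fat meal. With 6 per group and an assumed SD of change of 10-15 ms (not in the documents), the 90% CI half-width for impaired versus control is 1.812 × SD × √(2/6), or about 10-16 ms. This stands: the result would remain descriptive, but it would describe the relevant exposure.

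**Moving the ECG drops a later safety check.** This is a real cost, and whether to keep a 96 h ECG for monitoring is the sponsor's decision.

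**Conclusion.** The point holds as a limit on what this endpoint can show. The only scheduled post-dose ECG is at 96 ± 4 h, with parent concentration at about 3% of peak on the 18 h half-life, about 2-8% over the half-lives the documents imply, and about 10-19% if AUC rises 50-100% through lower clearance. Provided any QT effect follows concurrent parent concentration, the Day 5 change and its 90% CI carry little information about QT near peak exposure in renal impairment.

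The conclusion rests on that condition, on roughly first-order elimination and, for the renal range, on clearance being the only thing that changes. It does not extend to saying that the endpoint could never register a drug effect, or that the plan intends the Day 5 result as reassurance about peak exposure. Neither document says so. The finding is a cheap improvement to a secondary endpoint and does not affect the primary PK analysis.

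**What to change.** Take the ECG used for the QTcF endpoint at the existing in-house 5 h or 6 h visit (01E or 01F), alongside the PK sample, instead of at Visit 01N. Update Protocol Sections 3.3.2, 6.2, 6.3.2, 7.1 and 10.5.3.4 and Appendix A, and SAP Sections 3.2.2 and 9.9, Table 2 and Table 80, to match.

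The cost is a schedule amendment. The number of ECGs is unchanged, and each QTcF value gains a paired concentration near peak. The downside is that there is no scheduled ECG at the end of PK sampling, although vital signs, safety laboratory tests and adverse event review stay at 96 h. Keeping a 96 h ECG as well, for safety monitoring, is for the sponsor to decide.

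If the timing cannot change, add one sentence to Protocol Section 3.3.2 and SAP Section 9.9 saying that the Day 5 QTcF change is not evidence about QT at peak exposure. That costs nothing, but it only records the limit and does not remove it.
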